4.6 Data Sources

- **4.6.1**. **Case Report Forms**: Because the study is conducted remotely and via a mobile app, it will not employ formal case report forms. Instead, surveys will be delivered via the mobile app in two forms: 1. During initial on-boarding, patients will answer a series of surveys delivered in consecutive order. These surveys will remain on the app (and will be the first thing a patient sees when they interact with the app) until they are completed. 2. Short surveys will be delivered via push notifications from the app.
- **4.6.2 Eureka Technology Platform**: Individuals will enter data via the Eureka mobile app. As with the great majority of research in the Health eHeart Study that is obtained remotely and from patient self-entry, the study will rely on a framework of patient reported data. Patients who fail to complete surveys will be sent reminders via app-related push notifications or SMS text messages.

4.7 **Data Access and Reports** During the study, the Eureka data management team at the University of California, San Francisco will have access to the raw study data from all data sources. Standardized reports will be generated to allow the study team to monitor recruitment and retention, progression through the phases of the N-of-1 trial and/ or data tracking arm, completion of surveys, and responses to study activity notifications. These outputs will be visualized in real-time using the Eureka administrative portal and reports can be printed or provided as a PDF as needed. In coordination with the study statistician, the Eureka data management group will also prepare reports for the data safety and monitoring board (DSMB). These reports will include data on: accrual, data quality and completeness, study withdrawals, rates of completion of N-of-1 trials, and hospitalizations and emergency room visits.

At the conclusion of the study, the data coordinating center will work with the study biostatistician to prepare the analytic data files to be used in the final analysis. The study statistician will only be obtaining and using de-identified data for this project. Please see attached letter from Brown IRB regarding the non-human subjects waiver.

5. Analytic Plan

5.1 Overview

Figure 2 details the study design for Aim 2 which is designed as an RCT to compare use of N-of-1 studies vs. symptom surveillance (data tracking alone) using comparable mHealth technology in both study arms. Working with the HeH patient stakeholders, we will design a menu of triggers that people with AF may select to test in their own personal N-of-1 study. This menu will include approaches for modifying triggers including alcohol, caffeine, exercise (frequency and intensity), sleep, liquid intake/dehydration,

meal size, sleep position (e.g., lying on left side), beverage and food temperature, or choices at the option of the patient. These N-of-1 protocols will involve 6 randomly assigned treatment periods (each 1-week in duration) of exposure (trigger "on") and elimination (trigger "off").

Figure 2

5.2 Sample Size for Number of Study Patients

As those with at least moderate AF severity have an AFEQT score of 58 ± 19^{19} and the most modest of therapies typically improves this score by a mean of 5-10, we have powered this study conservatively to detect an improvement of 5 points in the AFEQT. We estimate 239 patients in each group would provide 80% power to detect this small, yet still clinically meaningful difference.

5.3 Randomization to Treatments

Completion of the electronic consent via the Eureka portal will trigger 1:1 randomization to the N-of-1 or the symptom surveillance conditions. The randomization schema will be conducted within the Eureka platform and communicated directly to patients via the mobile app.

5.4 Analysis

5.4.1 Comparison of N-of-1 to data tracking

The experimental design for Aim 2 is a two-arm randomized trial comparing N-of-1 vs. symptom surveillance. The primary endpoint is AF severity via the AFEQT from baseline to 10 weeks. Differences between treatment groups will be compared using analysis of covariance with the 10 week measurement as the outcome and the baseline measurement as covariate. We will also test for an interaction between treatment and baseline AFEQT in order to measure possible treatment effect heterogeneity. The average frequency, duration and severity of AF episodes per week during the final month of each patient's enrollment will be secondary outcomes. Their group means will be compared with a t-test. Additional secondary outcomes will include safety events: hospitalizations, emergency room visits, stroke, myocardial infarctions and heart failure. The main analysis will treat each of these as a binary outcome indicating the incidence of any event. We will also investigate models for multiple Version 1.0 5/12/17

events per person if these are common. We will check for balance in covariates across the randomized groups and will adjust for any imbalances by including those covariates in regression analyses and reporting the adjusted treatment effect as a secondary analysis. The null hypothesis of no difference will be tested at a significance level of 0.05.

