1.2 Study Objective

Test the comparative effectiveness of N-of-1 trials versus data tracking alone to identify and eliminate individual- level triggers and reduce AF frequency and severity.

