1.5 Study Procedures

Randomization/Baseline evaluation: Potential participants will be identified via the Health eHeart Study and the StopAfib.org patient advocacy organization and reached out to via email campaigns. Of note, invitations will be extended broadly to include friends family and acquaintances of those participants. Patients may also be recruited directly from UCSF clinics or other web-based sources of potentially interested atrial fibrillation patients. The study email campaign will contain an overview of the study. If the patient is interested in participating in the study there will be a link for the participant that will take them to the mobile app store to

download the Eureka app. Potential participants will be prompted to register an account and will complete an inclusion/ exclusion criteria survey within the Eureka app. If eligible, they will continue on to the study consent form (Appendix B). Upon completion of the electronic study consent, Eureka will randomize participants to either the N-of-1 or the symptom surveillance arm of the study with a 1:1 allocation ratio.

Participants will then be asked to complete baseline data collection which will include basic demographics, medical history, and current atrial fibrillation medications. After baseline data collection, the study team will ship AliveCor devices to study participants over a period of two weeks. At the end of this two week period, participant will be prompted to visit the Eureka application to complete a device consent and then will be instructed to download the AliveCor app and link their AliveCor device to their Eureka account. All participants will then complete the Atrial Fibrillation Effect on QualiTy of Life survey (AFEQT) (Appendix A). Once they complete the survey, the app will show participants which study arm they have been randomized to and prompt them to begin the appropriate study activities.

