N-of-1 Trial arm: Patients will use the Eureka mobile application and AliveCor device to execute at least one N-of-1 trial with the goal of identifying and better controlling their AF triggers. Each N-of-1 trial will last a total of 6 weeks and will include up to 3 periods of trigger exposure and 3 periods of trigger elimination with each exposure/elimination period lasting 1 week. Patients will be randomly assigned a sequence of trigger exposure and elimination periods such that they receive each treatment in each two-week block. During each N-of-1 trial, patients will track daily AF duration and severity, daily mood and sleep quality, daily AliveCor tracings and daily trigger exposure. At the end of each trial, patients will be able to review their trial results which will include visualizations of their daily AF symptom and trigger tracking over time. After completing a trial, patients will be instructed to implement any lifestyle changes they deem appropriate based on what they learned from the results of their trial. Patients will implement these changes for a period of 4 weeks during which they will continue to track AF episode duration and severity via the app. At the end of the 4-week lifestyle change period, patients will complete the Atrial Fibrillation Effect on Quality of Life survey (AFEQT) (Appendix A) and will then have the option of testing another trigger or ending their study participation.

Symptom Surveillance arm: Patients will use the Eureka app and AliveCor device to record daily AF duration and severity, daily AliveCor readings and daily mood and sleep quality for a period of 10 weeks. Patients will be able to visualize their AF, sleep and mood data in real time and will receive a weekly summary of their data via the Eureka app. At the end of the 10-week data tracking period, patients will complete the AFEQT survey and will then have the option of either ending their study participation or crossing over to the N-of-1 trial arm to test their triggers.

Primary Study Aim:

To test the comparative effectiveness of N-of-1 trials vs. data tracking alone to identify and eliminate individual level triggers and reduce AF frequency and severity as measured by the atrial fibrillation quality of life scale (AFEQT)

Secondary Aims:

- Using individual N-of-1 trials, identify modifiable exposures that increase the risk for an AF episode on an individual-level.

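### The final-month AF frequency, duration and severity comparisons make no use of the baseline AF information collected before the arm is shown

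*SAP*

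**What the plan says.** **Objective.** Protocol 1.2 sets out to identify and eliminate "individual- level triggers and reduce AF frequency and severity". The SAP's Primary Study Aim (section 2) narrows this to "reduce AF frequency and severity as measured by the atrial fibrillation quality of life scale (AFEQT").

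**AF episode outcomes between arms.** "The average frequency, duration and severity of AF episodes per week during the final month" are secondary outcomes in SAP 5.4.1, and "Their group means will be compared with a t-test". Protocol 1.7.2 plans the same test for frequency and severity. SAP 4.3 defines these outcomes from the final month only.

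**Primary outcome.** In the same SAP paragraph the AFEQT is analysed by "analysis of covariance with the 10 week measurement as the outcome and the baseline measurement as covariate".

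**Order of events before the intervention (Protocol 1.5).** Participants register in the app, consent, are randomized, and give demographics, medical history and AF medications. Then: "After baseline data collection, the study team will ship AliveCor devices to study participants over a period of two weeks". They link the device and complete the AFEQT survey of Appendix A. "Once they complete the survey, the app will show participants which study arm they have been randomized to", and it then prompts the activities of that arm. No AF tracking is described during the wait.

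**Covariates.** SAP 5.4.1 will adjust for covariates found to be imbalanced, and reports this as a secondary analysis.

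**The concern.** AF episode counts, durations and severity are the outcomes closest to the wording of the Protocol objective. Neither document's inclusion criteria set a minimum or maximum episode frequency, so a wide spread between participants is likely. An unadjusted comparison of final-month means carries all of that spread as noise. The SAP avoids this for the AFEQT by conditioning on baseline, but not for these outcomes.

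Two things are at stake. One is precision on the AF episode comparisons. The other is descriptive: with no pre-intervention episode log, neither arm's change in episode frequency or duration can be estimated.

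**Working it through.** **1. The plan's own figure.** SAP 5.2 gives 239 per arm for 80% power to detect 5 AFEQT points with SD 19. Taking alpha 0.05 as two-sided (the SAP does not say), n = 2(1.96 + 0.84)² × 19²/5² = 227 per arm, or 228 by exact t-test. At 239 per arm the exact t-test has 81.9% power, so the stated 80% is met. This figure concerns the primary outcome; no power is stated for the AF episode outcomes.

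**2. What exists at baseline.**

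| Information | Before the arm is shown? | Used for the AF episode outcomes? |
|---|---|---|
| Daily AF yes/no, duration, severity | Not described | No baseline value |
| AFEQT score | Yes (Protocol 1.5) | No; used for the AFEQT only |
| Currently in AF; time since last episode (Appendix A) | Yes, in the AFEQT survey | No |

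**3. Value of a baseline covariate.** Adjustment leaves a fraction 1 − r² of the variance. The effective sample grows by 1/(1 − r²). With 239 per arm, two-sided 0.05 and 80% power, the detectable difference in SD units is √(2/239) × (1.96 + 0.84) × √(1 − r²) = 0.256 × √(1 − r²). The documents give neither r nor an SD for these outcomes, so r is an assumption.

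| r | Variance removed | Effective sample | Detectable difference (SD) | Power for 0.256 SD |
|---|---|---|---|---|
| 0 (current t-test) | 0% | 1.00 | 0.256 | 80% |
| 0.25 | 6% | 1.07 | 0.248 | 82% |
| 0.3 | 9% | 1.10 | 0.244 | 84% |
| 0.5 | 25% | 1.33 | 0.222 | 90% |
| 0.7 | 49% | 1.96 | 0.183 | 97.5% |

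**4. Price of adjusting for the items already collected.** AF status has seven categories (currently in AF, plus six last-episode answers), so six coefficients, and AFEQT adds one. Seven coefficients in 478 patients cost about 7/478 = 1.5% of variance. The adjustment gains once the covariates together explain more than about that.

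**5. What a two-week self-report log might give.** Suppose AF days are Poisson around a person-specific rate with mean m per week and coefficient of variation CV, and let V = (CV × m)². For a two-week baseline and a four-week outcome, r = V/√[(V + m/4)(V + m/2)].

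| CV | Range of r for m from 0.25 to 1 |
|---|---|
| 0.7 | 0.25 to 0.57 |
| 1 | 0.41 to 0.73 (0.58 at m = 0.5) |
| 1.5 | 0.61 to 0.86 |

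The lowest rate, 0.25 a week, is about the once-a-month frequency mentioned in the Appendix E survey introduction. The model covers counts only, and assumes that AF days do not cluster and that rates stay constant from run-in to final month. If underlying rates correlate only 0.7 over that gap, r² is multiplied by 0.7² = 0.49; at CV 1 and m = 0.5 the variance removed falls from 33% to 16%.

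**6. Severity.** With CV 1 and gamma-distributed rates, the chance of no AF day in two weeks is 1/(1 + 2m): 67%, 50% and 33% at m = 0.25, 0.5 and 1. Those participants would have no baseline episode severity, because SAP 4.3 averages severity over episodes.

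**The case against.** The strongest reply is that nothing is invalid. Randomization makes the comparison of final-month means unbiased, the trial's question is between arms, and these outcomes are secondary with no power claimed. The SAP ties its aim to the AFEQT, which has a baseline and is adjusted for it. SAP 5.4.1 also plans balance checks and adjusted secondary analyses. Most of this stands, and it limits the point to precision. It does not answer the point: adjustment triggered by imbalance is not prespecified adjustment, the gain comes from a covariate's prognostic strength whether or not it is imbalanced, and Table 2 does not list the last-episode item.

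A reader might infer three stronger things that the documents do not support.

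- *That there is no baseline AF record at all.* Baseline AFEQT and the Appendix A items are recorded. Appendix A also says its respondents complete an AF survey and an AF severity scale, and SAP 3.1 (Step 5) retains an AF severity survey. Table 2 does not list these companion surveys, so their use here is unclear.
- *That chance differences in AF burden cannot be seen or corrected.* The AFEQT and recency items allow a partial check and correction.
- *That a run-in would give a clean measure of change.* During the wait participants have no AliveCor. Afterwards they have a device that detects AF and are told to use it daily, so self-reports may shift when it arrives.

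The run-in also has a cost to the primary outcome. Daily tracking is the core of the comparator. Starting it during the wait puts up to two weeks of tracking before the baseline AFEQT, whose symptom items recall four weeks, and lengthens tracking from 10 to about 12 weeks. This is equal in both arms, so it does not bias the contrast, but it changes what the primary baseline measures.

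**Conclusion.** The point holds as one about precision on secondary outcomes. No baseline record of AF episode frequency, duration or daily severity is planned, and the final-month means are compared without any baseline covariate although relevant ones are already in hand. There is no bias, and the primary AFEQT analysis is unaffected.

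The gain is r² of the variance: from 6% at r = 0.25 (1.07 times the effective sample) to 49% at r = 0.7 (1.96 times). It rests entirely on an assumed r, and is smaller if AF rates drift. For the recency item r is unknown and could be small; the case there is that the adjustment is nearly free. The run-in is a debatable option. It relies on the order of events in Protocol 1.5, since SAP 5.3 gives no time at which patients learn their arm.

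**What to change.** **Main change.** In SAP 5.4.1 replace the t-tests for final-month AF frequency, duration and severity with ANCOVA or linear regression on arm, baseline AF status and baseline AFEQT, prespecified rather than conditional on imbalance. Build AF status from Appendix A as a currently-in-AF category plus the time-since-last-episode categories, because the latter question is asked only when current AF is No. Add the item to Table 2, and bring Protocol 1.7.2 into line. The unadjusted difference can be reported alongside. The cost is wording only, with no new data and no added burden.

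**Option.** Start the existing self-reported daily AF yes/no and duration prompts when the baseline surveys are complete, run them until the arm is shown, and hide summaries in that window. Use the resulting AF-day rate and mean daily duration as covariates for the matching outcomes. If this is adopted, state its downsides: about two more weeks of prompts in both arms; tracking that begins before the baseline AFEQT; reports made without the AliveCor, and so usable as a covariate but not as a clean measure of change; and no baseline episode severity for many participants.

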Meta-Analysis of N-of-1 Trials: The collection of individual N-of-1 trials can be thought of as a set of studies whose results can be combined as in a meta-analysis. The data can be considered as a multilevel structure in which a set of patients is studied with each patient having a set of measurements. Standard multilevel mixed model methods will be used to estimate the average effect and variance within and across patients. Across patient values estimate the average effect in the population of patients studied, while the within-patient estimates describe an improved estimate of each patient's true effect assuming exchangeability across patients. We will fit these models using a Bayesian multilevel model with non-informative priors in order to obtain posterior distributions of the within and between effect sizes. We will then compare the multilevel patient estimates with those from the patient's data alone in order to determine how much the effects change and how much additional precision these estimates gain.

Analysis of Comparative Effectiveness: The experimental design is a simple two-arm randomized trial comparing N-of-1 vs. symptom surveillance. The primary outcome is the change in the AFEQT scale from baseline to 12 weeks. The mean change in each treatment group will be compared by a t-test. The average frequency and severity of AF episodes per week during the final month of each participant's enrollment will be the secondary

outcomes. Their group means will also be compared with a t-test. We will check for balance in covariates across the randomized groups and will adjust for any imbalances by including those covariates in regression analyses and reporting the adjusted treatment effect as a secondary analysis.

Missing Data: A major purpose of this aim is to determine the feasibility and usability of N-of-1 studies for actual application in clinical practice. Therefore, carefully documenting adherence and completion rates and predictors of each will be an important aspect of this study. Within the HeH study, we have found that >90 % of all AF HeH study participants complete all AF-related surveys, including the AFEQT. The primary analysis will be intent-to-treat which uses all participants as randomized. When no endpoint is available, we will assume no change. Further analyses will employ multiple imputation to fill in missing values, particularly in covariate-adjusted models ([name]-3).

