4.5 Potential Treatment Effect Modifiers

Within the N-of-1 experiments and in the comparison of N-of-1 to data tracking, it is recognized that external factors could influence willingness to adhere to a treatment assignment, could interact with the exposure and AF, and could affect AF episodes. Per suggestions from AF patients, we will therefore perform daily assessments of mood, sleep (the night previous) and stress. These will be obtained via push notifications and will therefore rely on patient self-report. Relationships between these factors and both treatments (N-of-1 and usual care) and outcomes will be investigated; given evidence of statistically significant relationships, results will be adjusted for these covariates.

1. **Medical History:** Characteristics as outlined in Table 2 collected at baseline by self-report include hypertension, diabetes, heart failure, history of cerebrovascular accident, first degree Version 1.0 5/12/17

family member with atrial fibrillation and history of atrial fibrillation and history of no disease other than atrial fibrillation.

- 2. **Demographics:** Basic demographic data as outlined in Table 2 including age, gender, race/ethnicity, height, weight, and education level will be collected both to describe the population of patients and to assess for heterogeneity of treatment effects at the population level.
- 3. **Current medications:** Current medications being taken including antiarrhythmic drugs, aspirin, Plavix, warfarin or others as noted in Table 2 will be recorded.
- 4. **Mood and sleep:** Patient self-report on mood and sleep will be collected via short survey on the Eureka app on a daily basis.

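### The arm comparison should not be adjusted for daily mood, sleep or stress measured after randomisation, and the secondary adjusted analysis should use baseline covariates named in advance rather than those found imbalanced.

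*SAP*

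**What the plan says.** **Primary model.** SAP 5.4.1 compares the arms by "analysis of covariance with the 10 week measurement as the outcome and the baseline measurement as covariate". No other covariate enters. Protocol 1.7.2 instead gives a t-test on the change score. That difference is a separate matter, and neither primary analysis uses the rules discussed here.

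**Baseline imbalance rule.** SAP 5.4.1 then has the analyst inspect how covariates fall between the arms, and states that the team "will adjust for any imbalances by including those covariates in regression analyses". The resulting estimate has secondary status. Protocol 1.7.2 has the same instruction, to "adjust for any imbalances by including those covariates in regression analyses". Neither document lists the covariates to be checked, says what counts as an imbalance, or refers to their relation with the outcome. In the SAP the sentence comes after the AF frequency, duration, severity and safety outcomes, so it is not confined to AFEQT.

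**Daily-measure rule.** SAP 4.5 covers both the N-of-1 experiments and the comparison of the two arms. It provides for daily self-report of mood, the previous night's sleep, and stress. Their relationships with treatment and with outcome are to be examined, and "given evidence of statistically significant relationships, results will be adjusted for these covariates". It does not say whether this concerns the primary result, a secondary one, or both.

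**What is available at baseline.** SAP 4.5 says: "Characteristics as outlined in Table 2 collected at baseline by self-report include hypertension, diabetes, heart failure, history of cerebrovascular accident". On drugs: "Current medications being taken including antiarrhythmic drugs, aspirin, Plavix, warfarin or others as noted in Table 2 will be recorded". Protocol 1.7.2 names lone AF, sex and race in advance, but only for interaction tests.

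**The concern.** The two rules fail for different reasons.

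The SAP 4.5 rule adjusts a randomised comparison for variables that the intervention can change. Apart from chance, an association between arm and a daily measure taken during follow-up is an effect of the arm. The rule therefore tends to trigger where the measure is most likely to be on the pathway to the outcome. The adjusted figure then no longer estimates the effect of being assigned to N-of-1 testing. What is at stake is bias in the estimated treatment effect.

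The imbalance rule chooses covariates by the accident of allocation. Under sound randomisation any imbalance is chance, so a strong predictor that happens to be balanced is left out and an irrelevant variable that happens to differ goes in. With no list and no criterion, the model is settled after the data are seen. If the adjusted and primary estimates differ, a reader cannot tell correction from selection. What is at stake is precision and credibility in a secondary analysis.

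**Working it through.** **1. The daily measures against the rest of the plan**

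| Element | Where | Consequence |
|---|---|---|
| Sleep and mood are recorded daily throughout the study in both arms | Protocol 1.4; SAP Table 2 | Measured after randomisation |
| Sleep is among the triggers that may be tested | Protocol 1.5; SAP 5.1 | The intervention may act through sleep |
| Mood categories include anxious and stressed | SAP Table 2 | Mood is close to part of the outcome |
| AFEQT scores worry and anxiety about AF, with a four-week recall | Protocol Appendix A | Covariate and outcome overlap in content and in time |

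Suppose the true total effect is 5 AFEQT points (SAP 5.2) and a share m passes through sleep or mood. In a linear model with no confounding between that measure and the outcome, the adjusted estimate centres on 5 × (1 − m). The documents give no basis for m, so no figure is offered. With confounding, the adjusted estimate need not even equal the direct effect.

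**2. The plan's sample size, used as the base for step 5**

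Inputs from SAP 5.2: difference 5, SD 19, power 80%. Alpha is 0.05 (SAP 5.4.1), taken as two-sided because sidedness is not stated.

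n per arm = 2 × (1.960 + 0.842)² × 19² / 5² = 2 × 7.849 × 361 / 25 = 226.7, so 227 (228 by the exact t-test). The stated 239 is about 5% higher, on the safe side, and gives 82.0% power. Although 227 / 0.95 = 239, no 5% allowance is stated. Nothing below depends on this gap.

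**3. How often chance imbalance would trigger the rule (illustration only)**

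SAP Table 2 has 22 baseline-only modifiers. Assume each is tested at 5% and all are independent:

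- expected number flagged = 22 × 0.05 = 1.1
- chance of at least one = 1 − 0.95²² = 0.676, or 68%
- with 10 covariates, 1 − 0.95¹⁰ = 0.401, or 40%

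The documents state no 5% criterion, and several of the 22 are clearly related (for example sex and gender identity, or coronary disease and heart attack).

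**4. What the imbalance rule does to the estimate**

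Simulation, 4,000 replicates per setting: 478 participants, 20 independent covariates of which 3 predict outcome, SD 19, imbalance taken as p < 0.05. R² is the assumed share of outcome variance explained by the three predictors. Baseline AFEQT was not modelled separately.

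| R² | Power, unadjusted | Power, imbalance-chosen | Power, pre-specified | Mean SE, imbalance-chosen | Mean SE, pre-specified |
|---|---|---|---|---|---|
| 0.1 | 81.2% | 81.4% | 84.6% | 1.75 | 1.66 |
| 0.2 | 81.4% | 81.6% | 88.9% | 1.74 | 1.56 |
| 0.3 | 80.9% | 82.1% | 92.2% | 1.73 | 1.46 |

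The unadjusted mean SE was 1.74 throughout. With no true difference, type I error under the imbalance rule was 4.4-4.6%. The rule does not inflate error when applied mechanically, and it recovers almost none of the available precision.

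**5. What a named set could be worth**

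The documents give no R² for these covariates, so 5-10% of residual variance is an assumption. The equivalent gain in participants is 1 / (1 − 0.05) = 1.05 to 1 / (1 − 0.10) = 1.11, about 5-11%. On SD 19 with 239 per arm, using SD × √(1 − R²), power moves from 82.0% to 83.9% (R² = 0.05) or 85.8% (R² = 0.10). These power figures give no credit for baseline AFEQT, which is already in the SAP's primary model.

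**The case against.** The strongest reply is that the primary analysis is safe. SAP 5.4.1 fixes the ANCOVA in advance, baseline AFEQT is probably the strongest single predictor, and the imbalance rule feeds only a secondary estimate. That stands. A reader might infer from the data-driven wording that the primary result or its error rate is compromised. The documents do not support this, and the simulation shows no inflation under the rule. It did not examine unrestricted analyst choice or the SAP 4.5 rule.

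A second reply is that the plan speaks of checking balance, not of testing it. That also stands: the 68% illustrates one possible criterion and does not measure this plan.

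Third, the documents call the Table 2 variables modifiers and give no prognostic strength for them. A reader might take them to be established predictors of 10-week AFEQT, or take the 5-11% to be a gain for the primary test. Neither follows. The gain is assumed and belongs to the secondary adjusted estimate.

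Fourth, SAP 4.5 does consider relation to outcome, so the criticism that prognostic value is ignored does not reach it. That is correct. Its defect is the timing of the measurements. It could also be argued that SAP 5.4.1 governs and keeps mood and sleep out of the primary model. That reading is reasonable, but SAP 4.5 expressly includes the arm comparison and sets no such limit, so the two sections leave the matter open.

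**Conclusion.** The point holds in two parts of unequal weight.

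1. **SAP 4.5, the more important.** Adjusting the randomised comparison for daily mood, sleep or stress can remove part of the effect under test. This rests on the documents' own description of when and what is measured. The size is unknown, and the documents do not show that such an adjustment would replace the primary estimate.
2. **SAP 5.4.1 and Protocol 1.7.2.** Choosing covariates by chance imbalance gives up precision and leaves a choice open until after the data are seen. The effect is confined to the secondary adjusted analysis. The value of a named set, about 5-11% more participants for that estimate, depends wholly on an assumed 5-10% of further residual variance explained.

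Both should be changed. Neither invalidates the primary analysis.

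**What to change.** - **SAP 4.5:** state that the randomised arm comparison will not be adjusted for mood, sleep or stress recorded after randomisation. Keep these measures for description and for analyses within the N-of-1 trials.
- **SAP 5.4.1 and Protocol 1.7.2:** delete the imbalance rule from both. Name a short set of baseline covariates from Table 2, chosen on expected prognostic value and fixed before unblinding. Age, sex and antiarrhythmic drug use are candidates. If lone AF is considered, note that it is partly defined by age. Add the set to baseline AFEQT in the adjusted AFEQT model.
- **Other secondary outcomes:** apply the same set to AF frequency, duration and severity, so that removing the rule does not leave them without a stated adjusted analysis. Say whether adjusted analyses of the safety events are intended.
- **Balance:** report baseline characteristics by arm descriptively, and do not let them decide the model.

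The cost is wording in the SAP and the protocol. No new data are needed, and the sample size and the SAP's primary ANCOVA stay as they are.
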